8.2. Screening Assessments

These evaluations occur to determine if the Immunology Center patient is eligible for the study.

- HIV infection status will be obtained from the medical record.
- ART Adherence will be assessed using self-report and viral load: participants who are less than 100% adherent during the past six months and/or those with a viral load (obtained from the medical record) > 20 copies/mL will be eligible.
- Psychologically distress will be measured using the PHQ-4¹¹⁵; only individuals scoring ≥ 2 on the PHQ-4 will be included in the study.
- Recent sexual risk behavior assessed with self-report.
- Prior training in mindfulness, meditation, or related mind-body techniques will be assessed using self-report.
- Severe hearing impairment not allowing phone delivery will be self-reported and corroborated by the PD.
- Telephone access will be assessed by self-report.
- Literacy will be assessed by the SILS.
- Suicidal ideation will be assessed by questions on recent suicidal thoughts and plans. Individuals endorsing 1 or more of these items will be assessed further by use of the suicide protocol (Appendix 5).
- Additional foil questions about other health factors (e.g., smoking, alcohol use) will be included to decrease the likelihood of potential participants figuring out eligibility criteria.

8.3. Baseline Assessments

FEASIBILITY

To assess feasibility the following will be recorded: number of screened, eligible, consented and randomized participants; number of patients who refuse participation and reasons for refusal.

EFFICACY OUTCOMES

1. Medication Adherence

Consistent with NIH (e.g., PA-14-335)¹²⁴ and expert recommendations,¹²⁵⁻¹²⁸ we will employ a multi-modal assessment of medication adherence: self-reported ART adherence, objectively reported ART adherence, and a biological health-related indicator (viral load).

- *Self-report:* we will use the Wilson 3 item Self-Report Adherence measure, a recently developed and validated 3-item measure.¹³⁰
- *Objective:* phone-based unannounced pill counts.¹³¹⁻¹³³ Unannounced phone-based pill counts are reliable and valid.¹³²⁻¹³⁶ Field studies show high concordance between phone-based and home-based number of pills counted (Spearman's rho = .995, $p < .001$) and percentage of pills taken ($r = .997$, $p < .001$).¹³² Concordance between participants defined as 90% adherent to their medications by the phone count and home count was 95%, Kappa coefficient = .995. Adherence determined by unannounced cell phone-based pill counts also corresponds with VLs at a similar magnitude observed between unannounced home-based pill counts and VL.¹³¹ Use of a phone-based method has the additional advantage of being consistent with the phone-based MT intervention we are evaluating. A detailed protocol for the phone-based unannounced pill count protocol can be found in Appendix 3. This protocol has been provided by [name], our consultant.
- *Biological indicator: Viral load:* Although not a direct measure of adherence, VL is closely aligned with adherence.¹³⁷⁻¹³⁹ Participants will provide blood specimens for performing VL lab work. Samples will be collected using standard phlebotomy and processed at Lifespan laboratories.

2. Sexual Risk Behavior

Also consistent with the NIH Consensus Panel and recommendations from HIV prevention experts, we will employ a multi-modal assessment of sexual risk behavior with self-report, medical chart review, and laboratory testing.

- *Self-report:* This information will be collected using a self-reported survey developed according to standard strategies.¹⁴⁰⁻¹⁴³ We will collect information using items that we have used in previous studies,¹⁴⁴⁻¹⁴⁷ namely, number of male and female sexual partners; number of occasions of protected and unprotected oral, anal, and vaginal sex; partner type and partner serostatus over previous 3 months.
- *Medical chart review for clinical diagnosis of STI:* This information will be collected from medical, consistent with current guidelines¹⁴⁸ and prior work.^{145,149} This information is necessary to capture STIs that have been treated between visits¹⁵⁰ because successfully treated bacterial infections will not be detected with laboratory testing.
- *Laboratory-diagnosed STI:* this data will be collected as a proxy of risk sexual behavior. We will collect blood, urine, rectal, and pharyngeal specimens, and test these using at Lifespan laboratories using standard processing methods. STI testing will be supervised by Co-I [name], an infectious disease physician. Detailed procedures about specimen collection and

lab testing will be included in the Manual of Procedures. We will collect:

- Urine specimens for urethral (men) and cervical (women) Gc, CT, and Trichomoniasis
- Pharyngeal swabs for Gc.
- Rectal swabs for Gc and CT.

Laboratory results will be reviewed by the [name] and the PD. If there is a positive test the participant and his or her Immunology Center provider will be notified. The Immunology Center provider will advise the participant on treatment options (if applicable). If the STI is reportable, it will be reported to the Health Department as required by law.

MODERATORS AND PARTICIPANT DESCRIPTORS

Research suggests a number of person factors that may be associated with adherence to ART and safer sex. We will seek to balance comprehensiveness of the data set with participant burden. We will look for precise measures of constructs with the fewest items that yield reliable and valid estimates of the constructs.

- *Demographic characteristics* (e.g., sex assigned at birth, gender identity, age, race/ethnicity, relationship and employment status, income, educational attainment) will be assessed using standard questions developed in previous research with this population.
- *Perceived physical health* will be assessed with a single item from the Medical Outcomes Study General Health Survey.^{154,155}
- *Medical history* will be obtained from patient's medical record, and will include: date of initial HIV diagnosis, likely mode of contracting HIV, length of time since initiating ART, VL and CD4 counts, adherence to medical appointments (# of missed appointments, if any), AIDS diagnosis (yes/no, date), number of HIV-related hospitalizations, medical and psychiatric comorbidities and current medications. Our hospital system now maintains an electronic medical record, and data will be corroborated as appropriate.
- *Social support* will be measured using 12 items from the Medical Outcomes Study Social Support Survey, a 19 item survey used to measure how perceive social support (i.e., family, friends, and significant other).
- *Sleep* will be measured using the Pittsburgh Sleep Quality Index, a 7 item measure.
- *Alcohol use* will be assessed with the Alcohol Use Disorders Identification Test (AUDIT),¹⁶³ widely used in healthcare settings; scores of ≥ 8 indicate hazardous drinking, and scores ≥ 16 suggest alcohol use disorder; and PhenX Measures for Lifetime Use, 30-Day Frequency, and Maximum Drink in 24 Hours.
- *Other drug use* will be measured with the PhenX Substances-Lifetime Use, Substances-30 Day Frequency and DAST-10.
- *Smoking* will be measured with questions about lifetime smoking and past 30 days.
- *Food Security* will be measured using the U.S. Household Food Security Survey, a 6 item index.

MEDIATORS

- *Mindfulness* will be assessed with the FFMQ-15, a measure of trait (dispositional) mindfulness comprised of 15 items.
- *Depression* will be assessed using the PHQ-9.

- *Anxiety* will be assessed using the GAD-7.
- *Perceived Stress* will be measured with the 4-item Perceived Stress Scale (PSS),^{117,175} which assesses the degree to which participants perceive circumstances as stressful in the last month. Higher scores indicate greater levels of perceived stress.
- *Impulsivity*. The Barratt Impulsiveness Scale (BIS-11)^{176,177} has 5 factors (attention, motor, self-control, cognitive complexity, perseverance, and cognitive instability impulsiveness) and is widely used.

8.4. Post-Intervention and Follow-up Assessments

Two additional assessments will take place (a) post-intervention (within two weeks of finishing the program) and (b) at 3 months post-intervention (within 12 weeks (+/- 2 weeks) after finishing the program):

- Feasibility
 - Retention rates; drop-out counts and reason for dropping out will be maintained by the RA.
 - Adherence to Mindfulness Training and Health Coaching
 - Session attendance will be recorded at each session by the instructor using an attendance log.
 - Individual practice at home will be self-reported during each session.
- Acceptability
 - Satisfaction Survey¹⁷⁸ reporting how informative, interesting, and helpful the MT was; how likely they are to continue practicing after the training; whether they would recommend it to other PLWH; and whether they have suggestions for how we might improve it. Participants will rate the interventions on a scale from 0 to 6.
- Qualitative data collection
 - At each assessment, participants will be asked to participate in an interview to solicit information about their experiences. They will be asked open-ended questions about their experiences. The semi-structured qualitative interview guide can be found in Appendix 4.
- Efficacy (measures described at Baseline)
 - Adherence to ART
 - Self-reported adherence
 - Unannounced pill counts
 - Viral Load
 - Sexual Risk
 - Self-report of risk behavior
 - STI (chart diagnosis)
 - STI (lab-diagnosed)
- Moderators (measures described at Baseline)
 - Perceived health
 - Sleep
 - Alcohol Use
 - Substance Use
 - Smoking
- Mediators (measures described at Baseline)
 - Mindfulness

- Depression
- Perceived stress
- Impulsivity
- Anxiety

9. DATA COLLECTION

9.1. Data Sources

With participant consent, information about concurrent medical conditions and history as well as current medications will be collected from electronic medical records.

9.2. Data Safety

Electronic data will be stored in password protected data files accessible only to authorized project personnel including the PIs, Data Systems Analyst, Statistician and the PD. All data files will be automatically backed up daily. Paper data will be stored in locked file cabinets. Data containing identifiers (e.g., name, address, phone number of participants) will be stored on password-protected secure servers separately from de-identified study data (e.g., surveys, screeners).

9.3. Data Collection

The PD will collect data via in-person interviews at each assessment. Electronic data capture technology will be used for direct data entry during the interviews; clinical data will be entered by the PD from the abstraction forms into electronic version of the abstraction forms. Any ambiguity in the response to a question will be brought to the attention of the Data Systems Analyst for clarification. If the Data Systems Analyst is unsure how to code the response, the matter will be brought to the attention of the PI.

9.4. Qualitative Data Collection

Data from qualitative interviews will be collected using audiotapes and observer/interviewer notes. Audio recordings will be analyzed using a framework matrix and will be reviewed by study staff. At the conclusion of the study recordings will be destroyed.

10. DATA MANAGEMENT

10.1. Tracking Systems

Prior to beginning participant recruitment; the Data Systems Analyst will develop a tracking system using Filemaker software. The tracking system will help the PD in ensuring that all procedures are followed, interventions are adhered to, and assessments administered in a timely fashion. The tracking system will include all steps included within the Recruitment, Treatment and Follow up phases of participant participation in the trial.

10.2. Data Entry and Storage

Our major data management and analysis needs for the proposed project can be met by using a Pentium-based microcomputer. The data systems analyst will conduct data management under the supervision of the study biostatistician and the PIs. De-identified data will be exported directly into study datasets. Depending upon the analytic question, either STATA 14 (Stata

Corporation) or SAS statistical software will be used for analyses, as determined by the study biostatistician, [name].

Electronic data will be stored in password protected data files accessible only to authorized project personnel including the PIs, Data Systems Analyst, Statisticians and PD. All data files will be automatically backed up daily. Paper data will be stored in locked file cabinets. Data containing identifiers (e.g., name, address, phone number of participants from ACCESS files) will be stored on password-protected secure servers separately from de-identified study data (e.g., surveys, screeners).

The Data Systems Analyst will work with project statistician [name] and the PIs to ensure that data are cleaned prior to analysis. When ready for analysis, he will provide a STATA database of collected data to the statistician.

11. QUALITY CONTROL AND QUALITY ASSURANCE

11.1. Treatment Fidelity

Procedures are described in section 7.5.

11.2. Training

All staff involved in data collection will be trained and certified regarding their competence. This includes training on administration and scoring of all questionnaires as well as on reviewing assessment instruments immediately for omissions. When information is missing or incomplete, the PD will contact participants to obtain the necessary information. A *manual of operations* will be developed during the study start-up period that explicitly describes the specific procedures related to data collection and quality assurance. At study beginning, the first 10 participants will have their data audited to make sure there are not any systematic problems with regards to entry. This preliminary audit process will reveal any possible problems at the onset as opposed to the end of the study, which would result in more work cleaning the data.

Staff will receive extensive training in maintaining patient confidentiality, supervised by [name], a licensed clinical psychologist with 30 years of research and clinical experience in sexual health, HIV, substance use, and related socially sensitive topics. Training will focus on procedures for making sure data are not accessed by individuals outside of the research team, keeping identifying information separate from data, and not disclosing participant information or participant names to individuals outside of the research team. Staff will be assigned readings about confidentiality and research ethics; readings will be discussed with [name]. All staff will complete on-line NIH- and Hospital-based ethics training. Staff will also receive extensive confidentiality training, which will involve reading, online videos and other training materials, and discussing scenarios in which confidentiality could be breached. Staff will be required to sign an agreement to keep all patient information confidential. In addition, staff will receive training in duty to warn and duty to report child abuse. They will be told to immediately contact one of the investigators if a participant threatens to hurt him/herself or someone else, or if a participant reports child abuse.

Staff will also receive training in study policies and procedures, the need for clinical sensitivity in working with patients, gender and developmental sensitivity, and cultural and sexual orientation competence. Staff will role play recruitment and assessment sessions with the investigators, to demonstrate competence with the study protocol. When hiring project staff, we will recruit individuals with previous research experience who demonstrate a good understanding of the importance of participant confidentiality and research ethics, and evince personal integrity. We,

and the Miriam Hospital Human Resources Department, will check personal and professional references to be sure that all research staff have high personal standards regarding confidentiality and clinical sensitivity, as well as an ability to maintain the scientific responsibilities entrusted to them.

11.3. Data Monitoring

With supervision from the PIs and the Study Biostatistician ([name]), the Data Systems Analysts ([name]) will ensure that entered data accurately represent data collected. He will conduct error-checking procedures quarterly on all data to ensure their accuracy. Data entry systems developed using Access will include appropriate skip patterns and parameter limits to ensure that data are entered accurately (e.g., item response formats from 1-5 will not permit entry of other numbers). Data entry systems will be tested to ensure that these constraints are working correctly prior to entering real data. Microsoft ACCESS employs automatic checks for values that are out of range or represent errors of logic. Outliers will be corrected if possible with verification from participants.

Quantitative data will be cleaned prior to analysis and then made available to the study statisticians for analysis. [name] will be primarily responsible for the final outcome analyses and will assist in the preparation of manuscripts and reports.

11.4. Metrics

Direct entry of study data into electronic forms by the study participant and automatic parameter limits and error-checking procedures embedded into the Access system eliminate the need for re-entry of data and cross-referencing with paper copies, as well as auditing procedures. See Section 11.3 for data monitoring procedures.

11.5. Protocol Deviations

A *minor protocol deviation* is defined as an accidental and unintentional change, or non-compliance with the IRB approved research protocol that does not increase risk or decrease benefit or does not have a significant effect on the participant's rights, safety or welfare; and/or on the integrity of the data; for example, the need to reschedule a visit because the participant is traveling, or a follow up visit that occurred outside the protocol required time frame because of the participant's schedule. A *major protocol violation* is a divergence from the protocol that materially (a) reduces the quality or completeness of the data, (b) makes the Informed Consent Form inaccurate, or (c) impacts a participant's safety, rights, or welfare. Examples include: inadequate or delinquent informed consent; enrollment of non-eligible individuals; unreported or misreported serious adverse events; breaking of the blind; use of prohibited interventions; incorrectly collected or missing tests; multiple visits missed or visits outside permissible windows; intentional deviation from protocol, Good Clinical Practice, or regulations by study personnel.

Capture, documentation, and review. All protocol deviations will be captured using a protocol deviations tracking log as they occur. The PI will sign each form after it has been completed or immediately prior to a monitoring visit. If it has been signed with fewer than five deviations entered into it, the next identified deviation will be reported on a new page to ensure that all deviations have been reviewed by the PI. Pages will be numbered and stored in reverse chronological order in the study Regulatory Binder. At the conclusion of the study, the final page of the log will be identified by checking the box in the footer. ALL protocol deviations will be reviewed by the PI at weekly study staff meetings; SAE reporting procedures will be followed (see 4.5 and 4.6) if a protocol deviation results in a SAE.

Reporting. Minor protocol deviations will be included in IMC reports and in the TMH IRB continuing review application. Major protocol violations will be reported to the TMH IRB and to the NCCIH Program Officer.

Please note that retention, attendance are feasibility outcomes; consequently dropouts, missing session, and missing self-reported practice will not be considered protocol deviations. This information will be collected and monitored (as aggregate data and without breaking the PI blind status).

Protocol amendments. Please also note that given the pilot nature of this study, we may need to amend the original protocol in response to feasibility issues (e.g., if we realize that our eligibility criteria are too strict, unnecessary and negatively affect recruitment). If needed, we will submit an amended protocol to NCCIH for approval in the following cases: any change that may affect patient safety (e.g., change in eligibility criteria; change in risk, regardless of whether risk is increased or decreased); any change that changes scientific intent or study design, or affects human subject protection; addition/deletion of a site; addition/deletion of key study personnel; change of institution for key study personnel; change in enrollment targets. Amendments will also be submitted to the IRB in accordance with IRB policies at TMH.

12. STATISTICAL CONSIDERATIONS

12.1. Preliminary Analyses

Expertise. Co-Investigator [name], Ph.D., is a biostatistician who has extensive research experience in the context of behavioral medicine research, including research. She is familiar with the challenges associated with the analyses of count data, missing data, longitudinal data, and has used SAS, Stata, and other statistical packages for more than a decade. She will be responsible for the analysis of all quantitative data.

Preliminary analyses will examine comparability of participants in the MT and AC groups at baseline on demographic and other characteristics using Fisher or t-tests depending on the specific variable characteristics (categorical or continuous). We will examine the distributional properties of continuous variables to determine if normalizing transformations should be applied before conducting further analyses. If group differences are found for any variables, we will evaluate them and statistically control them in outcome analyses (e.g., employing them as covariates in analyses to control for their effects on the outcomes).

12.2. Primary Outcomes: Feasibility and Acceptability

Because this is a pilot study, analyses are not powered to detect treatment effects nor to formally test mediation or moderation. Any formal statistical testing will be only exploratory.

Feasibility. To determine feasibility of conducting a RCT, we will calculate the percentage of individuals who were: eligible; consented; accepted randomization; and returned for the post-intervention and 3-month follow-up. Based on our recent trials (R01-MH068171), we expect $\geq 80\%$ of all patients to return for the 3-month follow-up and will conclude the intervention is feasible if the follow-up rate is at least 80%. To determine feasibility of the MT and AC interventions, we will calculate the percentage of individuals who attended their intervention sessions. Based on previous research, we predict that $\geq 70\%$ of those assigned to a MT will complete all intervention sessions.

Acceptability. To determine the acceptability of the interventions, we will calculate means for the satisfaction surveys, and inspect responses. The intervention will be considered acceptable if $\geq 80\%$ of participants respond that they are satisfied with the intervention. We will also collect metrics (e.g., duration of calls, number of cancelled sessions). We will construe as evidence of acceptability, patients completing all ≥ 7 sessions, with call durations averaging 20 minutes per call, and with fewer than 3 rescheduled sessions.

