5. ELIGIBILITY

5.1. Population

This study will enroll 50 *HIV+* adult outpatients (25 per condition). The sample will be representative of the demography of the HIV epidemic and of the clinic outpatient population ($n = 1614$ outpatients with 70% male and 30% female; 60% White, 30% African American; 10% other/mixed; 25% Hispanic). We expect no difficulties recruiting 50 patients for this research.

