After all baseline assessments have been completed, the PD will randomly assign participants (1:1 ratio) to the MT or AC condition using a randomization schedule generated by the study biostatistician, [name]. The schedule will be generated using a permuted block randomization procedure with small, random-sized blocks. The allocation table will be password protected and saved to the CBPM secure drive. The unit of randomization will be the individual patient. We do not anticipate contamination between MT and AC, as patients will likely have no chance to exchange experiences about the interventions and instructors delivering the MT intervention will be different from those delivering the AC intervention.

Participants will be given the option to pick up intervention materials in person after randomization occurs or to have the materials mailed to them. Intervention materials for the MT condition consist of a compact disc with audio recordings of the mindfulness instructor's voice as well as a box of raisins to be used during mindfulness sessions and daily practice. Scripts of these recordings are located in Appendix 1 of this protocol. The compact disc doesn't contain the name of the study nor any identifying information about the study or the participant. Intervention materials for the AC condition consist of a packet of material pertaining to the session topics (i.e. nutrition, sleep) that is available to the public on the internet. These materials were chosen from websites such as the Centers for Disease Control and the

American Heart Association. Intervention materials for both MT and AC condition do not mention HIV or HIV status.

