7.1. Study Outcomes

Primary outcomes: feasibility and acceptability.

Feasibility: Key metrics will include the number of screened, eligible, consented and randomized participants; retention rates; session attendance; and individual mindfulness practice. We will consider either condition feasible under the following conditions:

- 1) If we achieve retention rates of 80% at the final follow-up visit
- 2) If patients attend at least 70% of the planned sessions
- 3) If patients report to have completed 70% of the assigned individual home practice exercises
- 4) Intervention session calls lasting approximately 20 minutes
- 5) Fewer than three rescheduled intervention calls

Acceptability: We will assess the following domains:

- 1) Participants' experience in the study (qualitative data collection)

- 2) Participants' ratings of the interventions on a satisfaction survey. The intervention will be considered acceptable if ≥80% of participants responds that they are at least somewhat satisfied with the intervention.

Secondary outcomes:

Preliminary estimates of effect size of mindfulness training vs. attention control on changes from baseline ART adherence, risky sex behaviors as well as on hypothesized mediators (i.e., mindfulness, depression, perceived stress, and impulsivity) will be assessed. We expect that the mindfulness training condition will achieve larger positive changes in ART adherence and risky sexual behaviors compared to the attention control condition.

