12.6. Sample Size

Because effect size estimates based on small samples have large SDs and wide confidence intervals (CIs),¹⁸⁴ we will use these pilot data only to gauge whether MT effects are encouraging, to examine distribution of the outcomes, and to inform future analytic approaches. The choice of the proposed sample size ($n = 50 - 25$ participants per condition) was based on practical considerations.

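### Section 12.2 draws a conclusion about the intervention from an 80% follow-up rate whose only stated denominator is both arms together, whereas section 7.1 applies the 80% retention criterion to each condition

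*Combined protocol and SAP*

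**What the plan says.** Section 7.1 (Study Outcomes) sets the criteria for the primary feasibility outcome and makes the condition the unit of judgement: "We will consider either condition feasible under the following conditions". The first of its five criteria is "If we achieve retention rates of 80% at the final follow-up visit". The other four cover session attendance, home practice, call length and rescheduled calls.

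Section 12.2 opens its feasibility paragraph with trial-level percentages: "To determine feasibility of conducting a RCT, we will calculate the percentage of individuals who were: eligible; consented; accepted randomization", followed by return for the post-intervention and 3-month visits. Citing the team's recent trials, it then expects at least 80% "of all patients to return for the 3-month follow-up and will conclude the intervention is feasible if the follow-up rate is at least 80"%. Next it turns to the two interventions, but with a different measure: "To determine feasibility of the MT and AC interventions, we will calculate the percentage of individuals who attended their intervention sessions". It specifies no retention rate by arm.

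The planned size is 50 "adult outpatients (25 per condition"), allocated 1:1 (section 6.2: "the PD will randomly assign participants (1:1 ratio) to the MT or AC condition"). Section 12.6 says the size was chosen on practical grounds. Its remark on imprecision, "Because effect size estimates based on small samples have large SDs and wide confidence intervals", concerns effect sizes and not the feasibility percentages.

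**The concern.** The two sections do not give the same rule for a primary outcome, and nothing elsewhere in the document says which governs. An analyst working from section 12 would most naturally compute one follow-up percentage over all 50 participants, compare it with 80%, and report the result as a finding about the intervention. An analyst working from section 7.1 would compute two percentages and judge MT and AC separately.

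The choice matters when retention differs between arms. A pooled rate measures how well the trial holds participants. It cannot show whether MT does, because good retention in AC can offset losses in MT. At stake is a stated conclusion that MT is feasible when its own arm misses the retention criterion in 7.1. Leaving the denominator open also means it could be chosen after the data are seen.

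**Working it through.** **Plan's own figures.** There is no power or precision calculation to reproduce. The sizes are consistent: 25 + 25 = 50 under 1:1 allocation.

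**Inputs from the documents.** 25 per condition (section 5.1); threshold 80% (sections 7.1 and 12.2).

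**Inputs assumed.** True retention in each arm, which the documents do not give. A range is shown. Participants are taken to be retained independently.

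**Step 1: turn the threshold into counts.**
- Pooled, 12.2 as written: 0.80 × 50 = 40, so at least 40/50.
- Per condition, 7.1: 0.80 × 25 = 20, so at least 20/25.

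**Step 2: splits at the pooled boundary that fail 7.1 for MT.** The fewest MT participants that still pass is 40 minus the number retained in AC.

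| AC retained | Fewest MT that pass pooled | MT rate | MT under 7.1 |
|---|---|---|---|
| 25/25 | 15/25 | 60% | fails |
| 24/25 | 16/25 | 64% | fails |
| 23/25 | 17/25 | 68% | fails |
| 22/25 | 18/25 | 72% | fails |
| 21/25 | 19/25 | 76% | fails |
| 20/25 | 20/25 | 80% | passes |

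**Step 3: how often the rules disagree in this direction.** Let X ~ Binomial(25, p_MT) and Y ~ Binomial(25, p_AC), independent. Then

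P(pooled passes and MT fails) = Σ over x = 15 to 19 of P(X = x) × P(Y ≥ 40 − x).

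Worked at 70/90:
- x = 15: 0.0916 × 0.0718 = 0.0066
- x = 16: 0.1336 × 0.2712 = 0.0362
- x = 17: 0.1651 × 0.5371 = 0.0887
- x = 18: 0.1712 × 0.7636 = 0.1307
- x = 19: 0.1472 × 0.9020 = 0.1327 (0.1328 from the rounded factors shown)
- Sum: 0.395

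The same calculation over a range:

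| True MT/AC | P(pooled passes) | P(MT ≥ 20/25) | P(pooled passes, MT < 20/25) |
|---|---|---|---|
| 90/90 | 0.991 | 0.967 | 0.028 |
| 85/85 | 0.880 | 0.838 | 0.089 |
| 80/80 | 0.584 | 0.617 | 0.102 |
| 70/80 | 0.261 | 0.193 | 0.122 |
| 60/90 | 0.247 | 0.029 | 0.218 |
| 75/85 | 0.584 | 0.378 | 0.242 |
| 75/90 | 0.754 | 0.378 | 0.382 |
| 70/90 | 0.584 | 0.193 | 0.395 |
| 70/95 | 0.760 | 0.193 | 0.567 |

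The rules can also disagree the other way: at 80/80, MT reaches 20/25 while the pooled rate misses 40/50 with probability 0.135.

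**Step 4: precision at the threshold.** Exact (Clopper-Pearson) 95% intervals: 20/25 gives 59% to 93%; 40/50 gives 66% to 90%.

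**The case against.** The strongest reply is that 12.2 does not clearly contain a pooled decision rule. Its reference to all patients qualifies what the team expects; the decision clause names no denominator, and 7.1 can supply one. The paragraph also separates two questions. Retention sits with eligibility, consent and acceptance of randomisation, as evidence on running an RCT, where a pooled rate is reasonable; feasibility of the two interventions is then taken up through attendance. On that view the fault is one loose phrase.

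Much of this stands. Neither section is fully explicit: 7.1 does not repeat the condition after its retention criterion either. But the sentence in 12.2 still draws a conclusion about the intervention from a rate whose only named denominator is everyone. If trial-level feasibility was meant, the conclusion needs rewording; if the intervention was meant, the denominator does.

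A reader might infer more than the documents support:
- **That the plan hides differential drop-out.** Drop-outs and their reasons are to be recorded at sessions and at both later assessments (Table 8.2), and a complete CONSORT diagram is planned (section 6.2). The imbalance would be in the data; only the stated rule could miss it. Nothing explicitly promises retention by arm, however.
- **That the rule alone would send a poorly retained arm to the R01 trial.** Section 2.2 only envisages that trial, and no section ties it to this criterion. Section 7.1 has four further criteria that a poorly retained arm might fail.
- **That the threshold equals the expected rate, so the rule is close to a coin toss.** Section 12.2 expects at least 80%. The single-arm pass probability of 0.617 holds at exactly 80%; it is 0.838 at 85% and 0.967 at 90%.
- **That the lack of confidence intervals is an error.** It is a reporting preference in a pilot that calls any formal testing exploratory.

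**Conclusion.** The point holds as an inconsistency in the rule for a primary outcome. Taken as written, 12.2 would call the intervention feasible with MT retention anywhere from 15/25 to 19/25, given enough AC retention, and every one of those MT results misses the criterion in 7.1.

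How often this would happen depends on retention rates that the documents do not give. Over the pairs examined, the probability runs from about 3% when both arms retain 90% to about 57% at 70/95. It is modest when the arms retain equally well (0.10 at 80/80) and rises with a gap in favour of AC. No single figure in that range should be quoted as the size of the problem.

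This is a should-fix point. The wording is partly ambiguous, the pilot is unpowered by design, and no safety or efficacy inference depends on the rule.

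**What to change.** In section 12.2, replace the sentence on the follow-up rate with one that matches 7.1: an intervention is concluded to be feasible on retention only if at least 80% of the participants randomised to that condition return for the 3-month follow-up (20 of 25 if 25 are randomised). Report the pooled follow-up rate separately and label it as trial-level feasibility. In 7.1, add that the retention rate is the rate within the condition.

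Optionally, print exact 95% intervals beside the per-arm rates, for example 59% to 93% at 20/25.

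The cost is one sentence in 12.2 and a few words in 7.1, with no new data, visits or participants. The downside is that each arm must pass on about 25 people, so the stated result is less precise and can be less favourable than a pooled one: at a true 80% in both arms, both reach 20/25 with probability 0.617 × 0.617 = 0.38, against 0.584 for the pooled rule.
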